4.1.2 Assessments within 7 days of the first dose

- 4.1.2.1 Physical examinations: height (only recorded at baseline) and body weight and current medical conditions.
- 4.1.2.2 Vital signs: body temperature, blood pressure and heart rate.

Note: If a subject presents with poorly controlled hypertension, defined as SBP \geq 140mmHg or DBP \geq 90mmHg, antihypertensive medication(s) should be initiated or adjusted with a goal to control the blood pressure to $<140/90$ mmHg.

- 4.1.2.3 ECOG PS
- 4.1.2.4 Clinical laboratory assessments.
- 4.1.2.5 12-lead ECG with QTc measurement
- 4.1.2.6 Baseline IL-6 and E-selectin assessment
- 4.1.2.7 Serum pregnancy test for women of childbearing potential.

4.1.3 Pre-dose Assessments on Day 1

- 4.1.3.1 Physical examination: to identify any changes in the subject's mental and medical conditions since baseline assessment that would make him/her ineligible for the study.
- 4.1.3.2 Blood pressure measurements: subjects must have a blood pressure reading of <140/90mmHg to be eligible.
- 4.1.3.3 ECOG PS: Any changes since baseline assessment should be recorded in the eCRF. Subjects having deterioration of ECOG PS to ≥ 2 will be excluded from the study
- 4.1.3.4 Review results of all the other baseline assessments to determine the subject's eligibility for the study. Any screening laboratory results outside the normal range will be repeated (prior to the first dose) at the discretion of the Investigator. All laboratory results must be within the values outlined in the Inclusion Criteria before the first dose of study drug.
- 4.1.3.5 Record all the medication(s) received within 2 weeks prior to the first dose of study medication and indicate if the medication is continuing.
- 4.1.3.6 Obtain archived tumor tissue samples for biomarker assessments (if available).
- 4.1.3.7 Obtain a blood sample for biomarker research. It is preferable to collect the sample on the first day of dosing but the sample may be collected at any time after first dose of investigational product. **Note:** a signed written informed consent for participating biomarker research must be obtained before collecting the blood sample for biomarker analysis.

5.0 Informed Consent

The investigational nature and objectives of the trial, the procedures and treatments involved and their attendant risks and discomforts, and potential alternative therapies will be carefully explained to the patient and a signed informed consent will be obtained.

5.1 Registration Requirements/Process

Once the signed informed consent has been obtained, all pretreatment evaluations have been performed, and patient's eligibility has been confirmed by the PI or collaborating investigator, a patient will be entered on study.

To register a patient, the research nurse or data manager must complete the eligibility/registration form and contact the PI, FAX a copy of the completed eligibility checklist, required pre-study tests (laboratory and pathology report), signed Informed Consent, signed Patients' Bill of Rights and HIPAA authorization form.

The nurse or data manager must log into the Electronic Data Capture (EDC) system and enter the eligibility/registration data for their reserved patient. The research nurse or data manager at the participating site will then:

- Verify eligibility
- Register the patient on study
- Assign a patient accession number

- Confirm the patient study number and dose level in the EDC system

6.0 Treatment Program

6.1 Treatment Overview

Treatment will be administered in an outpatient setting.

6.1.1 Schedule

Pazopanib should be taken at a dose of 800 mg oral daily, with 28 days of therapy constituting 1 cycle.

6.1.2 Criteria for Starting Subsequent Cycles

A cycle may be repeated every 28 days (+/- 3 days) if the patient has at least stable disease and continue to meet laboratory parameters as defined in the eligibility section.

6.2 Laboratory Studies

A local laboratory is to be used to perform all clinical laboratory assessments. Laboratory tests should be performed at baseline, at specified visits during the study, and at the follow-up visit, all as indicated in the Time and Events Table(s). Laboratory assessments may be performed within 3 days before the actual visit to allow flexibility in scheduling. Assessments may be performed more frequently if clinically indicated.

All laboratory tests with values that become clinically abnormal while the subject is participating in the study or within 28 days after the last dose of study drug should be repeated until the values return to normal or baseline.

Results for all unscheduled clinical laboratory assessments (i.e., haematology, TSH/T₄, coagulation parameters) should be recorded on an unscheduled laboratory form in the eCRF.

Hematology and Clinical Chemistry

Appendix A shows the hematology and clinical chemistry laboratory parameters that should be reported. Assays for hematology and clinical chemistry should be performed at baseline, every 4 weeks until 6 months, and then every 8 weeks thereafter. Hepatic assays should be performed at baseline, 2, 4, and 8 weeks, followed by every 4 weeks until 6 months, and then every 8 weeks thereafter.

Estimated creatinine clearance should be calculated using the Cockroft and Gault method.

Liver Function Tests

When a separate liver function test (LFT) panel is conducted, this panel should include the following: ALT, AST, alkaline phosphatase, GGT, and total bilirubin. A direct bilirubin level should be obtained if the total bilirubin level is greater than 1.5 x upper limit of normal (ULN). Liver chemistry threshold stopping criteria and dose modification guidelines have been designed to ensure subject safety.

Evaluation of Proteinuria

Proteinuria will be evaluated using the urine protein to creatinine ratio (UPC; see Appendix C). UPC will be determined at times specified in the Time and Events Table. If $UPC \geq 3$, then the dose modification table guidelines should be followed.

Coagulation Tests

Coagulation tests should be performed as specified in the Time and Events Table and also in response to an AE/SAE as clinically indicated. Coagulation tests include activated partial thromboplastin time (aPTT) and either prothrombin time (PT) or international normalized ratio (INR).

Lipid Tests

Lipid tests include cholesterol, high-density lipoprotein (HDL), low-density lipoprotein (LDL), and triglycerides. These tests should be performed as specified in the Time and Events Table. Additional testing may be performed if clinically indicated. In such a case, the subject should be in a fasting state.

Thyroid Function Tests

Thyroid function tests to assess thyroid stimulating hormone (TSH) and thyroxine (free T_4) should be performed as specified in the Time and Events Table. Unscheduled thyroid function tests (TSH and free T_4) may be performed if clinically indicated (e.g., if a subject develops signs and symptoms suggestive of hypothyroidism).

6.3 Studies Obtained During the Trial

Physical examination: to identify any changes in the subject's mental and medical conditions since baseline assessment that would make him/her ineligible for the study. This will occur at C1D15, C2D1 and monthly thereafter (1 cycle = 28 days).

ECOG PS: Any changes since baseline assessment should be recorded in the eCRF. Subjects having deterioration of ECOG PS to ≥ 2 will be excluded from the study. This will occur at C1D15, C2D1 and monthly thereafter (1 cycle = 28 days).

Obtain blood sample for IL-6 and E-selectin measurement. This will occur monthly while patients are on study.

Tumor assessments will be performed every 8 weeks (+/- 1 week) from randomization until the start of another anticancer therapy. A partial or complete response warrants confirmation no sooner than 4 weeks and no later than 6 weeks after its initial observation.

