6.5 Criteria for Removal from Study

Treatment may continue until one of the following criteria applies:

- Disease progression,
- Intercurrent illness that prevents further administration of treatment,
- Unacceptable adverse event(s),
- Patient decides to withdraw from the study,
- General or specific changes in the patient's condition render the patient unacceptable for further treatment in the judgment of the investigator, or
- Treatment delays of > 2 weeks due to adverse events.

Treatment may be interrupted within a cycle for up to 2 weeks and missed doses should be omitted. However, patients will be replaced if they do not receive at least 80% of the planned treatment in the first cycle of therapy.

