Grade 3 or 4	
Step 1. Interrupt IP until toxicity resolves to \leq Grade 2.
 
Step 2. Restart IP dose-reduced by 200 mg and monitor as clinically indicated.
 
If no recovery to \leq Grade 2 or recurrent Grade 3 or 4 thrombocytopenia, discontinue IP and follow-up per protocol

Anaemia: No specific dose reduction rules are indicated for anaemia unless due to haemorrhage or bleeding as noted above.	
Other Clinically Significant Adverse Events^b	
Grade 1	Continue IP; monitor as clinically indicated.

AE Terms & Descriptions	Dose Modification Algorithms
Grade 2 or 3, if clinically significant	Step 1. Interrupt IP until toxicity resolves to \leq Grade 1. Step 2. Restart IP dose-reduced by 200 mg and monitor as clinically indicated.
Grade 4	Discontinue IP and continue follow-up per protocol.
Prolongation of QTc Interval: If the QTc is prolonged, the ECG should be manually read to ensure accuracy of the reading. The values below refer to manually-read ECGs.	
QTc \geq 480 < 500 msec	Continue IP; monitor as clinically indicated.
QTc \geq 500 msec	Discontinue IP and continue follow-up per protocol.

- a. Well-controlled BP defined as mean SBP $<$ 140 mmHg and mean DBP $<$ 90 mmHg.
- b. AEs are graded according to NCI Common Terminology Criteria for Adverse Events 4.0 (NCI CTCAE 4.0).

Abbreviations: BP, blood pressure; IP, investigational product.

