9.1.7 Human Toxicities

The Comprehensive Adverse Event and Potential Risks list (CAEPR) provides a single, complete list of reported and/or potential adverse events (AE) associated with an agent using a uniform presentation of events by body system. In addition to the comprehensive list, a subset, the Agent Specific Adverse Event List (ASAEL), appears in a separate column and is identified with **bold** and *italicized* text. This subset of AEs (ASAEL) contains events that are considered 'expected' for expedited reporting purposes only. Refer to the 'CTEP, NCI Guidelines: Adverse Event Reporting Requirements'

http://ctep.info.nih.gov/protocolDevelopment/default.htm#adverse_events_aeers for further clarification. Frequency is provided based on 1019 patients. Below is the CAEPR for pazopanib (GW786034).

Version 2.1, April 13, 2009

Adverse Events with Possible Relationship to Pazopanib (GW786034) (CTCAE 4.0 Term) [n= 1019]			EXPECTED AEs FOR ADEERS REPORTING Agent Specific Adverse Event List (ASAEL)
Likely (>20%)	Less Likely (<=20%)	Rare but Serious (<3%)	Expected
BLOOD/BONE MARROW			
	Leukocytes (total WBC)		Leukocytes (total WBC)
	Lymphopenia		Lymphopenia
	Neutrophils/granulocytes (ANC/AGC)		Neutrophils/granulocytes (ANC/AGC)
	Platelets		Platelets
CARDIAC ARRHYTHMIA			
		Prolonged QTc interval (accompanied by Torsades de pointes)	
CARDIAC GENERAL			
		Cardiac ischemia/infarction	
Hypertension			Hypertension
		Left ventricular systolic dysfunction	
CONSTITUTIONAL SYMPTOMS			
Fatigue (asthenia, lethargy, malaise)			Fatigue (asthenia, lethargy, malaise)
	Weight Loss		
DERMATOLOGY/SKIN			
	Hair loss/alopecia (scalp or body)		Hair loss/alopecia (scalp or body)
Hypopigmentation			Hypopigmentation
	Rash/desquamation		Rash/desquamation
		Rash: hand-foot skin reaction	
ENDOCRINE			
	Thyroid function, low (hypothyroidism)		
GASTROINTESTINAL			
Anorexia			Anorexia
	Constipation		
	Dehydration		Dehydration
Diarrhea		Fistula, GI - Select	Diarrhea
			Fistula, GI - Select

Nausea		Perforation, GI - Select	Nausea
	Taste alteration (dysgeusia)		Perforation, GI - Select
Vomiting			Vomiting
HEMORRHAGE/BLEEDING			
	Hemorrhage, pulmonary/upper respiratory - Select	Hemorrhage, GI - Select	Hemorrhage, pulmonary/upper respiratory - Select
METABOLIC/LABORATORY			

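### Section 6.5 replaces patients with under 80% of cycle 1 treatment, but section 14.1.1 does not say how replacements enter the 14- and 28-patient decisions, and the bar stays at 5 responders

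*Combined protocol and SAP*

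**What the plan says.** **Replacement.** Section 6.5 (Criteria for Removal from Study) ends with the rule that "patients will be replaced if they do not receive at least 80% of the planned treatment in the first cycle of therapy". It names no qualifying or excluded reasons, so toxicity, early progression and withdrawal all count. A cycle is 28 days of daily dosing (6.1.1).

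**Decision rule.** Section 14.1.1 sets a Simon minimax design. Fourteen patients enter first; with at least 1 responder, accrual goes on to 28; with 5 or more responders, pazopanib is called promising, provided toxicity and survival are also acceptable. The discouraging rate is 8% and the encouraging rate 23%. The stated properties are 10% type I error, 80% power and a 31% chance of stopping at stage 1 when the true rate is 8%. Every eligible treated patient is in the response rate, and an unknown response counts as non-response. Replaced patients are not mentioned, and no bar is given for a total other than 28.

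**ECOG wording.** Section 6.3 and the synopsis say of an on-treatment fall in performance status that subjects reaching ≥ "2 will be excluded from the study. This will occur at C1D15, C2D1 and monthly thereafter". This repeats the Day 1 eligibility sentence in 4.1.3.3 ("2 will be excluded from the study"). The list in 6.5 has no performance-status threshold; its nearest item covers changes that in the patient's "condition render the patient unacceptable for further treatment in the judgment of the investigator". Section 6.1.2 lets a new cycle start "if the patient has at least stable disease and continue to meet laboratory parameters as defined in the eligibility section" and does not mention performance status.

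**The concern.** Read together, 6.5 and 14.1.1 let the number of treated patients exceed 28 while success still takes 5 responders. Each replacement adds another chance of a response against an unchanged bar. At 32 treated patients, 5 responders are 15.6% rather than the roughly 18% that the plan quotes.

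The alternative is to leave replaced patients out of the count. That contradicts the plan's own all-eligible-treated rule. Patients who stop in cycle 1 are also likely to be non-responders, so dropping them raises the apparent rate.

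Either way, the plan does not identify which 14 patients decide whether to continue and which 28 decide the final result. If that is settled after responses are known, the stated error rates no longer describe the trial.

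**Working it through.** **Inputs (14.1.1, 6.1.1, 6.5).** p0 = 0.08; p1 = 0.23; stage 1 n = 14, continue with ≥1 responder; N = 28; success with ≥5 responders; replacement below 80% of a 28-day cycle.

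**Formula.** With x the number of stage 1 responders,
P(promising) = Σ from x = 1 to 14 of Bin(x; 14, p) × P(Bin(N − 14, p) ≥ 5 − x).

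**Step 1: the plan's own figures.** At p = 0.08 and N = 28:
- x = 1: 0.3788 × 0.0214 = 0.0081
- x = 2: 0.2141 × 0.0958 = 0.0205
- x = 3: 0.0745 × 0.3100 = 0.0231
- x = 4: 0.0178 × 0.6888 = 0.0123
- x ≥ 5: 0.0035

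The sum is 0.0675, so type I error is 6.75%, within the stated 10% limit. At p = 0.23 the same sum is 0.8002. Stage 1 stopping at 8% is 0.92^14 = 0.311. The design reproduces, with 10% read as a ceiling.

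**Step 2: who is replaced.** 0.80 × 28 = 22.4, so a patient with fewer than 23 of 28 daily doses is replaced. A patient stopped at C1D15 has about 14/28 = 50% and qualifies. One who stops at C2D1 after a full cycle 1 does not. A patient who interrupts long enough without stopping does.

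**Step 3: replaced patients counted, bar at 5, 8% true among all treated.** The documents give no replacement rate, so k is an assumption.

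| Replaced, k | Treated, N | Type I error | 5/N |
|---|---|---|---|
| 0 | 28 | 6.75% | 17.9% |
| 1 | 29 | 7.6% | 17.2% |
| 2 | 30 | 8.5% | 16.7% |
| 3 | 31 | 9.5% | 16.1% |
| 4 | 32 | 10.5% | 15.6% |

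These keep the stage 1 look at 14 patients. If all k replaced patients enlarge stage 1 instead, k = 3 gives 9.7% and k = 4 gives 10.8%, so the limit is again passed at the fourth. If stage 1 is read on 15 or 16 treated patients, its stopping chance falls from 31.1% to 0.92^15 = 28.6% or 0.92^16 = 26.3%.

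**Step 4: replaced patients dropped, all of them non-responders, 8% true among all treated.** If a share d is replaced, the rate among those kept is 0.08/(1 − d). Putting that into the formula with N = 28:
- d = 5%: rate 8.42%, type I error 8.0%
- d = 10%: rate 8.89%, type I error 9.6%
- d = 15%: rate 9.41%, type I error 11.6%
- d = 20%: rate 10.0%, type I error 14.0%

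**Step 5: early stops cannot respond, 8% true only among adequately treated patients.** Responders then come from 28 adequately treated patients, whatever k is. If j of the k replaced patients fall in the first 14 treated, stage 1 has 14 − j who can respond. Over all j, for k = 1 to 4, type I error is 6.4% to 6.75%. There is no inflation.

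**The case against.** The strongest reply is that the inflation depends on what the 8% refers to. If it describes adequately treated patients and early stops cannot respond, step 5 shows that replacement leaves type I error at or slightly below 6.75%. That is correct, and the plan does not say which rate it means. Yet 14.1.1 counts all eligible treated patients, which makes the all-treated reading the natural one.

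A second reply is that the effect is small. The design has spare type I error, three counted replacements stay within 10%, and a fourth exceeds it by 0.5 points. A positive result also needs acceptable toxicity and survival. This stands and limits the size of the point. It does not supply the missing definition of the decision set.

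A third reply is that replacing under-treated patients is a deliberate choice that protects power. That is fair, and the cost of giving it up is shown under the fix.

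Three stronger readings are tempting but unsupported:
- *Section 6.5 replaces every early stop.* It does not; the rule turns on 80% of cycle 1 dosing (step 2).
- *The ECOG sentence removes patients from follow-up or from the denominator.* Sections 6.4, 11.0 (note d) and 12.2 keep follow-up going after treatment ends, and 14.1.1 keeps the patient in the response rate.
- *Section 6.3 forces removal of patients whom 7.1 would restart.* Fatigue ("Fatigue (asthenia, lethargy, malaise") is listed in 9.1.7 as likely, above 20%. For other events at "Grade 2 or 3, if clinically significant", section 7.1 advises interruption and then "Restart IP dose-reduced by 200 mg and monitor as clinically indicated". But 7.1 describes its contents as recommendations, 9.1.7 gives no grade for the fatigue, and no document gives a rate of decline to performance status 2. The investigator-judgment item in 6.5 can largely absorb a performance-status stop. What remains is mandatory wording in one place and discretionary wording in another.

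**Conclusion.** The point holds in a limited form. Followed as written, 6.5 and 14.1.1 allow a denominator above 28 with no matching bar, and the patients who decide each stage are not named. If 8% is the all-treated rate, type I error for the response criterion alone goes from 6.75% to between 7.6% and 10.5% with one to four counted replacements. If replaced non-responders are dropped, it is 8.0% to 14.0% when 5% to 20% are replaced. If early stops cannot respond and 8% applies only to the others, it does not rise.

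A reader might infer that the trial's type I error already exceeds 10%. The documents do not support that: with no expected replacement rate, the number of replacements is an assumption, and the limit holds through three counted ones. The case for a change is that the decision set should be fixed before responses are seen. The ECOG sentence is a minor wording matter and adds no weight to this conclusion.

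**What to change.** State in 6.5 and 14.1.1 that the stage 1 and final decisions use the first 14 and the first 28 eligible treated patients. Patients with under 80% of cycle 1 stay in, as non-responders if response is unknown, and replacements enter only a supplementary analysis. This follows the plan's own all-eligible-treated rule and keeps 28 patients, 5 responders, 80% power and 31% early stopping. It costs about one sentence and no added procedures.

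The downside is power. It stays at 80.0% if 23% is the rate among all treated patients. If 23% holds only for adequately treated patients and early stops cannot respond, only 28 − k of the first 28 can respond. Over all splits between stages, power is then about 77%, 74%, 70–71% or 66–68% for k = 1, 2, 3 or 4.

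As a wording correction, 6.3 and the synopsis should say that a fall to performance status 2 or more leads to discontinuation of study treatment under 6.5, with follow-up under 6.4. If a mandatory stop is intended, list it in 6.5.

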6.4 Post-Study Assessments

Any patient who is discontinued from study treatment for any reason will continue to have tumor assessments every 12 weeks (+/- 1 week) until the patient starts another anticancer therapy. The investigator or his/her designee will continue collecting information on the initiation of anticancer therapies until the date of data cutoff for the final analysis. All new anticancer therapy therapies after the last dose of treatment will be recorded on the appropriate CRF.

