- Obtain blood sample for IL-6 and E-selectin measurement. This will occur monthly while patients are on study.
- Tumor assessments will be performed every 8 weeks (+/- 1 week) from randomization until the start of another anticancer therapy. A partial or complete response warrants confirmation no sooner than 4 weeks and no later than 6 weeks after its initial observation. This confirmatory scan is considered outside of standard of care, and will be funded by the sponsor.

Post-Study Assessments

- Any research participant who is discontinued from study treatment for any reason other than PD will continue to have tumor assessments every 8 weeks (+/- 1 week) until the patient starts another anticancer therapy. The investigator or his/her designee will continue collecting information on the initiation of anticancer therapies until the date of data cutoff for the final analysis. All new anticancer therapy therapies after the last dose of treatment will be recorded on the appropriate CRF.
- All research participants will be followed for survival every 6 months.

Clinical Laboratory Assessments

All clinical laboratory assessments will be performed at City of Hope. Laboratory tests should be performed at baseline, at specified visits during the study, and at the follow-up visit, all as indicated in the Time and Events Table(s). Laboratory assessments may be performed within 3 days before the actual visit to allow flexibility in scheduling. Assessments may be performed more frequently if clinically indicated.

All laboratory tests with values that become clinically abnormal while the subject is participating in the study or within 28 days after the last dose of study drug should be repeated at the PI's discretion until the values return to normal or baseline.

Results for all unscheduled clinical laboratory assessments (i.e., hematology, TSH/T₄, coagulation parameters) should be recorded on an unscheduled laboratory form in the eCRF.

Hematology and Clinical Chemistry

Appendix A shows the hematology and clinical chemistry laboratory parameters that should be reported. Assays for hematology and clinical chemistry should be performed at baseline, every 4 weeks until 6 months, and then every 8 weeks thereafter. Hepatic assays should be performed at

baseline, 2, 4, and 8 weeks, followed by every 4 weeks until 6 months, and then every 8 weeks thereafter.

Liver Function Tests

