11.0 Study Calendar

	Pre-Study	Wk 1	Wk 2	Wk 3	Wk 4	Wk 5	Wk 6	Wk 7	Wk 8	Wk 9	Wk 10	Wk 11	Wk 12 ^c	Off Study ^d
Pazopanib 800 mg oral daily ^a		X	X	X	X	X	X	X	X	X	X	X	X	
Informed consent	X													
Medical history	X													
Concurrent meds	X		X-----										X	
Physical exam	X	X		X		X			X					X
Vital signs	X	X		X		X			X					X
Height	X													
Weight	X	X		X		X			X					X
Performance Status	X	X		X		X			X					X
CBC w/diff, plts	X	X		X		X			X					X
Serum chemistry ^b	X	X		X		X			X					X
EKG	X													
Adverse event evaluation			X-----										X	
Tumor measurements	X													X ^d
Radiologic evaluation	X													X ^d
B-HCG (women of child-bearing potential)	X													
Collection of IL-6, E-selectin	X					X			X					X
UPC	X	X				X			X					X ^d
Collection of tumor specimens	X													

a: Excepting adjustments for toxicity. b: Albumin, alkaline phosphatase, total bilirubin, bicarbonate, BUN, calcium, chloride, creatinine, glucose, LDH, phosphorus, potassium, total protein, SGOT[AST], SGPT[ALT], sodium. c: After week 12, on study, continue daily oral pazopanib therapy as previous and repeat assessments noted at weeks 1, 3, 5 and 9 every 28 days. d: Off-study evaluation. Follow up will be every 6 months for survival.

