14.1.2 Secondary Endpoints

Secondary endpoints include progression-free survival (PFS), overall survival (OS), and toxicity. Toxicity will use the CTCAE 4.0 and will summarize the worst grade per toxicity, per patient.

Additional secondary endpoints relate to biological correlates, including E-Selection, IL-6, the pre-metastatic niche density, pSTAT3, and baseline HGF. Because the nature of these secondary endpoints is exploratory, we will not consider the issue of multiple comparisons and the according adjustment of p-values.

To determine an association between E-selectin, IL-6 and pre-metastatic niche density, we will conduct a pairwise correlation test (linear regression). When the sample size is 28, the linear regression test of rho=0 (alpha = 0.050 one-sided) for one normally distributed covariate will have 80% power to detect a correlation coefficient of 0.435.

To determine if the biological correlates (e.g, IL-6, E-selectin, pSTAT3, and HGF), are associated with progression-free survival (PFS), we will fit univariate or multivariate Cox proportional hazards model and report the corresponding p-values. The same method will be employed to evaluate the prognostic effect of pre-metastatic niches.

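### Off-treatment tumor assessments are 8-weekly in section 6.3 and the synopsis but 12-weekly in section 6.4, so progression after stopping without PD has no single dating schedule

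*Combined protocol and SAP*

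**What the plan says.** Three places in the combined protocol and SAP govern scans after pazopanib stops.

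- Section 6.3: "Tumor assessments will be performed every 8 weeks (+/- 1 week) from randomization until the start of another anticancer therapy". The schedule ends at the next therapy, not at the last dose, so it runs on after pazopanib stops. The synopsis repeats this under its on-study assessments.
- Synopsis, post-study assessments: participants "will continue to have tumor assessments every 8 weeks (+/- 1 week) until the patient starts another anticancer therapy". This sentence is confined to those who stopped for a reason other than PD.
- Section 6.4: patients "will continue to have tumor assessments every 12 weeks (+/- 1 week) until the patient starts another anticancer therapy". Its population is wider: "Any patient who is discontinued from study treatment for any reason".

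The study calendar (section 11.0) does not settle the matter. Its off-study footnote gives only an off-study evaluation and then: "Follow up will be every 6 months for survival".

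Stopping without progression is foreseen. Section 6.5 lists, among other reasons, "Treatment delays of > 2 weeks due to adverse events". Section 14.1.2 gives the status of the outcome: "Secondary endpoints include progression-free survival (PFS), overall survival (OS), and toxicity".

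**The concern.** A patient who stops for toxicity is on an 8-week schedule under one section and a 12-week schedule under the next. Progression can be dated only when someone looks, so the interval is part of how PFS is measured. Patients who stop for PD already have their event, dated on the 8-week schedule. Only those who stop without PD could be moved to the coarser one, and on average their PFS would then look longer.

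PFS is also the outcome for the HGF, E-selectin, IL-6, niche-density and pSTAT3 objectives. The synopsis compares it with time to progression on the previous line. Section 14.1.1 makes a promising verdict conditional on acceptable survival endpoints, without a number. A schedule that differs with treatment status adds measurement noise to each of these uses.

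Separately, section 6.3 and the synopsis count the scan schedule from randomization. This single-arm trial has none, so the schedule has no defined origin.

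**Working it through.** **Can the texts be reconciled as written?** The windows are 8 ± 1 = 7 to 9 weeks and 12 ± 1 = 11 to 13 weeks. They do not overlap, so the tolerance does not explain the difference. Both are current text, and no order of precedence is given.

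**Is there a plan figure to reproduce?** No. The plan gives no PFS sample size, event count or power, and no stated figure depends on the scan interval. The sizes below rest on assumptions.

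**Mean detection delay in an affected patient.** Inputs: scan interval T of 8 or 12 weeks (documents). For illustration, the true median is taken as 4.9 months, or 21.3 weeks, the everolimus PFS in section 2.2. Progression is assumed exponential, with a stop at week 8.

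- λ = ln 2 / 21.3 = 0.0325 per week, so 1/λ = 30.7 weeks.
- Mean delay = T/(1 − e^(−λT)) − 1/λ.
- T = 8: 8/0.2292 − 30.73 = 4.2 weeks.
- T = 12: 12/0.3233 − 30.73 = 6.4 weeks.

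The difference is about 2.2 weeks. A simulation of 400,000 progression times gave 4.17 and 6.38.

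**Where the difference comes from.** After a stop at week 8 the scans fall at weeks 16, 24, 32 on the 8-week schedule and at 20, 32 on the 12-week one.

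| True progression (weeks) | Dated, 8-weekly | Dated, 12-weekly | Shift |
|---|---|---|---|
| 8–16 | 16 | 20 | +4 |
| 16–20 | 24 | 20 | −4 |
| 20–24 | 24 | 32 | +8 |
| 24–32 | 32 | 32 | 0 |

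Weighted evenly over the 24 weeks: (8×4 − 4×4 + 4×8 + 8×0)/24 = 2.0 weeks. The delay is a net average. Half of the span shows no delay, and 4 of the 24 weeks show earlier dating.

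**Whole-trial effect.** The documents give neither the true median nor the share stopping without PD. With assumed medians of 12 to 40 weeks, assumed shares of 10% to 50%, exponential stopping times and the 12-week clock running from the last scan, simulation gives:

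| True median (weeks) | Share stopping first | Added delay, affected (weeks) | Added delay, all patients (weeks) | Dated median, 8-weekly | Dated median, 12-weekly off treatment |
|---|---|---|---|---|---|
| 12 | 10% | 1.96 | 0.19 | 16 | 16 |
| 12 | 50% | 2.01 | 1.00 | 16 | 16 |
| 20 | 10% | 1.95 | 0.20 | 24 | 24 |
| 20 | 50% | 1.97 | 0.98 | 24 | 24 |
| 30 | 10% | 1.96 | 0.19 | 32 | 32 |
| 30 | 50% | 1.98 | 0.99 | 32 | 36 |
| 40 | 10% | 1.97 | 0.20 | 44 | 48 |
| 40 | 50% | 1.98 | 0.99 | 48 | 48 |

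Section 6.4 does not say when its clock starts. If it starts at the stop date, the added delay in affected patients is 2.2 to 2.7 weeks, and the all-patient figure at a 50% share is about 0.5 × 2.7 = 1.3 weeks.

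An assumed 40-week median sits exactly on a scan date. There the 8-weekly median itself came out as 40, 44 or 48 in different runs, and shifts reached about 4 to 6 weeks.

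**Median check at 21.3 weeks with a stop at week 8.** Dated by week 24 on the 8-week schedule: 1 − e^(−0.0325×24) = 54.2%. On the 12-week schedule, only progression by week 20 is dated by then: 1 − e^(−0.0325×20) = 47.8%. The overall share falls below 50% only if (54.2 − 50)/(54.2 − 47.8), about 66%, of those progression-free at week 8 stop then.

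**The case against.** The strongest reply is that the texts conflict but little follows from it. The primary endpoint is confirmed response, with its own confirmation scan. The interval could touch it only if a first response appeared after treatment stopped. PFS has no power, numeric threshold or control arm, and the biomarker analyses are declared exploratory. All versions stop scanning at the next anticancer therapy, so only patients who stop without PD and stay untreated are exposed. Section 12.2.1 asks for every effort to document objective progression after symptomatic deterioration, so scheduled scans are not the only route to a date. All of this stands and limits the size of the point. It does not tell staff which schedule to follow.

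A reader might infer more than the texts support:

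- **That the interval varies with the reason for stopping.** No passage distinguishes among non-PD reasons. The synopsis restriction leaves out only patients whose PFS event has already occurred, so that difference in population cannot change PFS.
- **That section 6.4 postpones every progression.** The first table shows some dated earlier and some at the same visit.
- **That about 2 weeks should be read against a 21-week median.** The figure applies to patients still progression-free at week 8. On the same assumption their median from the start is 8 + 21.3 = 29.3 weeks.

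**Conclusion.** The contradiction is real and the text leaves it unresolved. Its effect on PFS is modest: roughly 2.0 to 2.7 weeks of added apparent PFS, on average, in patients who stop without PD and remain off other therapy. Averaged over all patients it is about 0.2 to 1.0 week with the clock at the last scan. Median PFS is mostly unchanged for assumed true medians of 12 to 30 weeks. It can move where the median falls near a scan date or where about half or more stop early.

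Confidence is high for the inconsistency and lower for the sizes, which rest on exponential progression and on assumed medians and stopping shares. The documents do not support a claim that the primary analysis is compromised or that median PFS is generally biased. The point should be corrected because two instructions cover the same patients and the remedy is cheap.

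**What to change.** Reconcile the synopsis, sections 6.3 and 6.4 and the study calendar so that they state:

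1. one tumor-assessment interval, on and off treatment, for patients without PD. A common interval removes the difference. The 8-week interval is the one already stated in most places (section 6.3 and twice in the synopsis), and using it keeps PFS dating uniform;
2. one population for off-treatment scans: patients who stopped for reasons other than PD;
3. the existing end of scanning, the start of another anticancer therapy, unchanged;
4. a start date for the schedule that exists in this trial, such as first dose, in place of randomization.

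The cost is wording in those four places. If the 8-week interval is kept, a patient off treatment without PD has 24/8 = 3 scans instead of 24/12 = 2 in each 24 weeks. That is at most a few scans overall, which the synopsis already plans.
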